#### **Study Design**

This is an open-label, prospective, single-arm, single-center trial.

Objectives of this study include gaining experience with the experimental immunosuppression treatment regimen as well as to determine the proportion of subjects with insulin independence on this experimental regimen. Should these subjects demonstrate a very high rate of insulin independence at  $75 \pm 5$  days post-transplant (a rate of 40% or higher would be considered high by current standards), then this treatment may be considered for further study.

There is a larger parallel study with additional centers and more subjects (CIT-07) where subjects are treated with a standard Islet Transplant immunosuppression regimen. Subjects will be randomized to receive either the standard immunosuppression regimen under CIT-07 or the experimental immunosuppression in this protocol (CIT-05) at the time an islet preparation meets release criteria. The randomization will provide a mechanism for balance between the two studies and provide an objective selection of subjects to the two studies.

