#### 3. STUDY DESIGN

This is an open-label, prospective, single-arm, single-center trial of islet transplantation under a novel experimental regimen that replaces the CNI tacrolimus with the anti-B lymphocyte agent rituximab. We will use rituximab at a dose of 375 mg/m² per injection administered twice, one week apart. This is a modification of the dose used for non-Hodgkin's lymphoma in humans, which is 375 mg/m² per injection administered four times at weekly intervals,  and is less than the recommended dose use for the treatment of rheumatoid arthritis, which is 1000 mg twice 15 days apart.  In addition, this dose lead to sustained (>6 months) B lymphocyte depletion, and caused a low (4.3%) incidence of human antichimeric antibody (HACA) formation . Previous studies demonstrated that this dose is safe and depletes B lymphocyte in patients with high-titer panel reactive antibodies experiencing kidney allograft rejection and awaiting kidney transplantation .

Objectives of this trial include gaining experience with the experimental immunosuppression treatment regimen as well as to determine the proportion of subjects with insulin independence on this experimental regimen. Should these subjects demonstrate a very high rate of insulin independence at  $75 \pm 5$  days post-transplant (a rate of 40% or higher would be considered high by current standards), then this treatment may be considered for further study.

There is a larger parallel trial with additional centers and more subjects (CIT-07) where subjects are treated with the standard Islet Transplant immunosuppression regimen. Subjects will be randomized to receive immunosuppression under either CIT-07 or this study (CIT-05) at the time a suitable islet preparation is available for transplantation. The randomization will provide a mechanism for balance between the two studies and to provide an objective selection of subjects to the two studies.

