## 7. STUDY PROCEDURES

#### 7.1 Enrollment

This research study will be explained in lay terms to each potential research subject. The potential subject will sign an informed consent form before undergoing any screening study procedures. Subjects who are deemed eligible for the study (see sections 4.0) will be enrolled and assigned a unique subject number.

Once an Islet Transplant has been provided, the patient becomes a part of the intention-to-treat population. All transplanted subjects will be included in the primary analysis.

This will be an open-label, prospective, single-arm, single-center study. The addition of rituximab to the CIT-07 strategy with elimination of the CNI tacrolimus will be evaluated. All islets will be processed at the University of Pennsylvania where all subjects will be recruited.

Unless the study is terminated early, recruitment will continue until the maximum sample size is reached, at which point recruitment will be terminated. It is anticipated that accrual of subjects will take 24 months.

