#### 7.4 Randomization

Once a compatible islet prep becomes available, subject eligibility will be re-confirmed. Eligible subjects will be randomized on Day -2 relative to transplant, between CIT-05 and CIT-07. Subjects randomized will receive immunosuppressive therapy beginning on Day -2 (see Section 5 for full description of Study Treatment Regimen). Subjects will receive the initial islet transplant on Day 0 and will continue the immunosuppression regimen detailed in Section 5.

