# 7.5 Study Treatment Visits

The first study treatment visit will occur at the time a suitable islet preparation is available for transplantation. Once a suitable donor pancreas becomes available, the potential recipient will be notified and requested to arrive promptly (< 2-hours) for admission to the Kidney/Pancreas Transplant service of the Hospital of the University of Pennsylvania. On admission, blood work (glucose, HbA1c, electrolytes, creatinine, LFTs, CBC and differential, PT/INR, PTT, blood type and cross-match [including to HLA antigens]), urinalysis, EKG (unless performed in last 3 months), and chest X-ray (unless performed in last 3 months) will be performed. Once subject eligibility is confirmed by the above tests and the islet preparation meets release criteria, the induction of immunosuppression will begin on Day -2 with the administration of Thymoglobulin  $^{\otimes}$   $\pm$  rituximab, and the islet preparation will remain in culture for  $\sim$  48-hours until infusion on Day 0. On Day 0, once the islet preparation has been determined to still meet release criteria, the subject will proceed to the operating room for the transperitoneal infusion of islets to the portal vein under general anesthesia.

The immunosuppression and islet transplants will be delivered during the hospitalization as detailed in the above section titled Study Design. Blood work will be monitored every 6-12 hours for 48-hours post-infusion for glucose, electrolytes, creatinine, LFTs, CBC and differential, and levels of tacrolimus and rapamycin. BG will be performed every 2-hours during 12-hours post-infusion and dextrose and/or insulin will be administered as needed to maintain the BG 100-140 mg/dL. Thereafter, BG will be performed at least 7 times daily and basal (for insulin pumps) or glargine insulin used at  $\sim 30-50$  % of the pre-transplant dose for fasting BG > 100 mg/dL, and bolus (lispro or aspart) insulin used before meals for post-prandial BG > 140 mg/dL.

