				P	RCH	IVED	SAMI	PLES								
Serum		Х								X			Х	X	Χ	Х
PBMC & Plasma		Х								Х			Х	Х	X	Χ
RNA		Х								Х			Х	Χ	Χ	Х

 WL = Waiting List. BL = Baseline. Repeat assessments as indicated (i.e. yrly, q3mo), while subject is on the waiting list. All one-time WL/BL assessments should be completed on Day -2 whenever possible, but always prior to start of immunosuppression. For repeat WL/BL assessments, results from test done closest to the start of immunosuppression will be used as the baseline value.

<sup>2 Day 0 = the day of transplant. This SOE applies to the  $1^{st}$ ,  $2^{nd}$ , and  $3^{rd}$  transplant as applicable. The SOE is restarted at Day 0 for each subsequent transplant.

<sup>3 Informed Consent #1 includes information on CIT-07 and CIT-05 protocols.

<sup>4 Informed Consent #2 includes information specific to CIT-05. IC #2 must be signed immediately after randomization.

<sup>5 FOBT (take-home multiple sample method) or FIT w/in last yr, flexible sigmoidoscopy w/in last 5 yrs, double-contrast barium enema w/in last 5 yrs, colonoscopy w/in last 10 yrs. All positive tests should be followed up with colonoscopy.

<sup>6Retinopathy eval includes fundoscopic pictures for WL/BL assessments and Y1. Screening retinopathy evaluation should be done per site-specific standards.

<sup>7 Chemistry includes: Sodium, albumin, magnesium, chloride, potassium, alk phosphatase, total bilirubin, CO2, creatinine, ALT (SGPT), BUN, gamma GT, glucose, AST (SGOT), calcium, phosphorus.

<sup>8 Complete pregnancy test within 72 hours prior to randomization.

<sup>9 Serology includes: HBc Ab, HBs Ab, HBs Ag, HCV Ab, HIV, and HTLV-I/II. Do not repeat Hepatitis B tests if HBs Ab was previously positive.

<sup>10 Repeat only if previous test was negative.

<sup>11 Repeat for subsequent transplant(s).

<sup>12 Sample used for crossmatch may be obtained up to 60 days prior to the start of immunosuppression, as long as there is no evidence of infections or transfusions since the time the sample was drawn. Repeat crossmatch for subsequent transplants.

<sup>13 C-peptide should be done locally and drawn fasting, and twice between 1-3 hours post-prandial on Day 3 and Day 7 post-transplant.

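### The CIT-05-specific consent is signed after an open-label assignment, so subjects can refuse selectively once allocated, and the protocol contradicts itself on whether a decliner is counted

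*Protocol*

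**What the plan says.** Consent has two stages. Section 7.1 places the first before screening: "The potential subject will sign an informed consent form before undergoing any screening study procedures". Appendix 1, footnote 3, gives its scope: "Informed Consent #1 includes information on CIT-07 and CIT-05 protocols". The second form is specific to CIT-05. It sits in the waiting-list/baseline column of the schedule, but footnote 4 fixes its timing: "IC #2 must be signed immediately after randomization".

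Section 7.4 sets the allocation: "Eligible subjects will be randomized on Day -2 relative to transplant, between CIT-05 and CIT-07". Immunosuppression begins the same day, and the transplant follows on Day 0. There is no blinding; the synopsis states "This is an open-label, prospective, single-arm, single-center trial". Section 3 gives as one purpose of the randomization "to provide an objective selection of subjects to the two studies".

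The protocol gives two answers on who is analysed:

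- **Entry at transplant.** Section 7.1 says "Once an Islet Transplant has been provided, the patient becomes a part of the intention-to-treat population", and Section 10.1 likewise admits subjects to the final analysis once transplanted.
- **Entry at randomization.** Section 10.2.1 expects the primary endpoint for all randomized subjects and classifies a subject who withdraws consent to follow-up as a failure. Section 5.7.1 also counts one type of randomized but untransplanted case as a treatment failure: induction has been given and no adequate islet product arrives within 30 days.

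No section says how to count a subject who is randomized to CIT-05 and does not sign the second form.

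**The concern.** A signature that is required can be withheld. Here it is requested when subject and staff both know that the assignment is the rituximab-based, tacrolimus-free regimen. Preference, or an investigator's advice, can then influence who stays in CIT-05. If those who leave differ in prognosis from those who stay, the CIT-05 group is no longer the group that was randomized.

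Two analyses rely on the allocation. Section 10.2.2 compares insulin independence with CIT-07 subjects at the same center. Section 10.5 states that no suitable historical control rate exists and therefore bases early stopping on that same concurrent comparison. The primary analysis is a one-sample estimate and does not use the allocation, but its denominator depends on which of the two population rules is applied.

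The moment also leaves little time. Section 7.2 lets a candidate defer the first consent to a later visit in order to reflect and consult others. On Day -2 the subject has been "requested to arrive promptly (< 2-hours) for admission", an islet preparation is in culture, and induction starts that day.

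**Working it through.** **Following a decliner through the text.** A subject signs the first form, waits, is randomized to CIT-05 on Day -2, and does not sign the second form.

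- Sections 7.1 and 10.1: no transplant, so outside the intention-to-treat population.
- Section 10.2.1: randomized, so the endpoint is expected. If the refusal is read as withdrawal of consent to be followed, it counts as a failure. Refusing the second form is not obviously that, because the first form still stands.
- Section 5.7.1: does not apply, because no induction has been given and the islet product has not failed.

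The same subject is thus excluded, counted as a failure, or not covered, depending on the section read.

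**Inputs.** n = 12 and the 40% mark come from Section 10.4 and the synopsis. Section 10.5 sets looks at 9, 10 and 11 per group, with a one-sided exact test at p < 0.05. The number of decliners is not in the documents and is assumed to range from 0 to 4.

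**Reproducing the plan's figures.** The exact (Clopper-Pearson) 95% interval for 6/12 is 0.211 to 0.789, matching the stated 0.21 to 0.79. Exact enumeration of the three looks with a one-sided Fisher test gives a crossing probability of 0.028 to 0.033 for common true rates from 0.3 to 0.7. That agrees with the stated value below 0.05, provided the two groups remain comparable.

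**Primary estimate.** With x successes among 12 transplanted subjects and r decliners counted as failures, the estimate is x/(12 + r).

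| Decliners r | x = 6 | 95% CI | x = 5 | 95% CI |
|---|---|---|---|---|
| 0 | 6/12 = 50% | 0.21–0.79 | 5/12 = 42% | 0.15–0.72 |
| 1 | 6/13 = 46% | 0.19–0.75 | 5/13 = 38% | 0.14–0.68 |
| 2 | 6/14 = 43% | 0.18–0.71 | 5/14 = 36% | 0.13–0.65 |
| 3 | 6/15 = 40% | 0.16–0.68 | 5/15 = 33% | 0.12–0.62 |
| 4 | 6/16 = 38% | 0.15–0.65 | 5/16 = 31% | 0.11–0.59 |

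One decliner moves 6/12 by 50.0 − 46.2 = 3.8 points. If that subject would have succeeded, the figure is 7/13 = 54%, the same distance the other way.

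**Interim boundary.** With s total successes, the one-sided Fisher p for a successes in CIT-05 is the sum over x ≤ a of C(n₅, x)·C(n₇, s − x)/C(n₅ + n₇, s).

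- 4/9 against 8/9: (84·1 + 126·9)/C(18,12) = 1218/18564 = 0.066. Not crossed.
- One decliner added as a CIT-05 failure, 4/10 against 8/9: (120·1 + 210·9)/C(19,12) = 2010/50388 = 0.040. Crossed.

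This treats the decliner as additional to the nine. The protocol does not say whether such a subject counts as enrolled.

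**Final comparison (illustrative).** For 9/12 against 3/12 the two-sided Fisher p is 0.039. With 1, 2 and 3 decliners added to CIT-05 as failures it is 0.047, 0.062 and 0.121.

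**The case against.** Much of the other side's case stands.

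- **Consent is not first sought after randomization.** A reader of footnote 4 alone might infer that it is. Footnote 3 says the screening consent already covers both protocols, and Section 7.2 allows time to consider it. The second form is a second stage, and the two-hour call-in concerns travel to admission, not consent.
- **Decliners do not demonstrably vanish.** That follows from Sections 7.1 and 10.1, but Section 10.2.1 says otherwise, and Section 8.2.1 collects all adverse events from randomization. What the text establishes is a conflict, not silent exclusion.
- **Nothing says a decliner's place is refilled.** Section 6.1 states that subjects who terminate early are not replaced, though it does not say whether this reaches someone who declines the second form.
- **The primary estimate is single-arm.** Section 2.1 targets the rate among subjects treated with the regimen, so leaving out someone never treated is arguable. The CIT-07 comparison is acknowledged to have little power, and crossing the boundary only triggers a request for a DSMB recommendation.
- **CIT-07's consent procedure is not shown.** Refusal may be possible on both sides.
- **Withdrawal stays possible at any time** (Section 13.2), whenever the form is signed.

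These points limit the concern but do not remove it. The screening consent does not make the second signature optional. The conflict over who is counted lies within the protocol, so it is more than a detail left to the SAP. A conservative boundary at 9 to 11 per group can still be crossed or missed on one subject.

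**Conclusion.** The point holds in limited form. By requiring a study-specific signature after a known assignment, the protocol opens a route to selective refusal that works against its stated reason for randomizing. It also gives conflicting rules on whether a decliner is analysed. The analyses exposed are the secondary comparison with CIT-07 and the interim boundary; for the primary estimate, the effect is an unsettled denominator.

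One assumed decliner counted as a failure shifts 6/12 by about 4 points. A reader might put the shift at 1/12, or 8 points, but that is the weight of a subject inside the 12, and a decliner would be additional to them. The shift is small beside the 0.21 to 0.79 interval, yet enough to carry 5/12 below 40% or a 4/9 against 8/9 interim result across the boundary. All of these counts are illustrative.

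A reader might also conclude that the allocation is broken. The documents do not support that: they permit selective refusal and contain no evidence that it occurs. The case for change is that the remedy is cheap, not that bias has been shown.

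**What to change.** 1. Change Appendix 1, footnote 4, so that Informed Consent #2 is signed while the subject is on the waiting list and re-affirmed before randomization on Day -2. Randomize only subjects who accept either assignment.
2. Reconcile Sections 7.1 and 10.1 with Section 10.2.1: state one rule for a subject who is randomized but not transplanted, including one who declines the CIT-05 consent. One option is to count such subjects as failures, with a transplanted-only sensitivity analysis.
3. Report withdrawals between randomization and transplant by assigned study, CIT-05 and CIT-07.

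The cost is one signature moved earlier and a short text amendment. No visit is added, because Section 7.3 already brings waiting-list subjects back every 3 months. The downside is that some subjects will sign a consent for a regimen they are not assigned. Withdrawal after assignment remains possible, so the change narrows the route without closing it; the counting rule and the reporting deal with what is left.

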## **Appendix 2: Reduced Follow-up Schedule of Events**

Subjects withdrawn from study therapy should be followed according to the reduced follow-up schedule provided below. All reduced follow-up assessments should be scheduled relative to the day on which the study treatment is discontinued. The last follow-up visit will vary depending on when the subject discontinues study therapy and should be done at 1 year post the subject's **last** transplant.

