#### 3.1.1 Secondary Endpoints

#### **Efficacy Endpoints**

At  $75 \pm 5$  days following the first and final transplant(s):

- The proportion of insulin-independent subjects
- The percent reduction in insulin requirements
- HbA1c
- MAGE
- LI
- Ryan hypoglycemia severity (HYPO) score
- Basal (fasting) and 90-min glucose and c-peptide derived from the mixed-meal tolerance test (MMTT)
- β-score
- C-peptide: (glucose X creatinine) ratio
- Acute insulin response to glucose (AIRglu), insulin sensitivity, and disposition index derived from the insulin-modified frequently-sampled IV glucose tolerance (FSIGT) test
- Glucose variability6 and hypoglycemia duration derived from the CGMS

• Quality of life (QOL) measures

If a third transplant occurs less than 75 days after the second transplant, the 75 day endpoint data for the second transplant will not be collected.

At  $365 \pm 14$  days following the first transplant

- The proportion of subjects with an HbA1c <7.0% at Day 365 AND free of severe hypoglycemic events from Day 28 to Day 365 inclusive
- The proportion of subjects receiving a second islet transplant
- The proportion of subjects receiving a third islet transplant

A severe hypoglycemic event is defined as an event with one of the following symptoms: memory loss; confusion; uncontrollable behavior; irrational behavior; unusual difficulty in awakening; suspected seizure; seizure; loss of consciousness; or visual symptoms, in which the subject was unable to treat him/herself and which was associated with either a blood glucose level <54 mg/dL [3.0 mmol/L] or prompt recovery after oral carbohydrate, IV glucose, or glucagon administration.

At  $365 \pm 14$  days following the first and final islet transplant:

- The proportion of insulin-independent subjects
- The percent reduction in insulin requirements
- HbA1c
- MAGE
- LI
- Clarke score
- HYPO score
- Basal (fasting) and 90-min glucose and c-peptide (MMTT)
- β-score
- C-peptide: (glucose X creatinine) ratio
- AIRglu insulin sensitivity, and disposition index derived from the FSIGT test
- CGMS
- OOL
- The proportion of subjects receiving a second islet transplant
- The proportion of subjects receiving a third islet transplant
- The rate of subjects with an HbA1c  $\leq$ 7.0% and free of severe hypoglycemic events)

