# 5.7.2 Premature Discontinuation of Study Treatment (Transition to "Off-Protocol" Treatment)

Study treatment may be prematurely discontinued for any subject for any of the following reasons:

- 1. The subject is unwilling or unable to comply with the protocol.
- 2. The investigator believes that the study treatment is no longer in the best interest of the subject.
- 3. Graft Failure: Islet allograft failure will be defined as absence of insulin production by transplanted islets, as evidenced by absence of c-peptide. This will be determined by (1) undetectable c-peptide on random testing, followed by (2) undetectable c-peptide at baseline, and at 60 and 90 minutes after MMTT. C-peptide levels obtained in the course of the MMTT will be run at the core lab in Seattle, WA. All study treatment will be tapered and discontinued, at the discretion of the site Principal Investigator, when it is determined that graft failure has occurred.
- 4. An unexpected related SAE. The agent(s) to which the event is attributed will be discontinued.

Subjects who prematurely discontinue study treatment will remain in the study until normal termination, for the purpose of monitoring safety and efficacy parameters and will enter the reduced follow-up schedule outlined in Appendix 2. Data from these subjects will be used in the intent-to-treat analysis. These subjects are permitted to simultaneously enroll in a CIT or site-specific graft failure follow-up protocol, if available.

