# 6.2 Study Stopping Rules

# 6.2.1 Protocol Suspension and Review

Study enrollment at all participating clinical sites will be suspended pending expedited review of all pertinent data by the institutional review board (IRB), the National Institute of Allergy and Infection Disease (NIAID), the National Institute of Diabetes and Digestive and Kidney Diseases (NIDDK), and the NIDDK Data Safety Monitoring Board (DSMB), if any one of the following occurs:

- 1. The Medical Monitor finds any unexpected fatal or life-threatening AE possibly related to the use of the test therapy;
- 2. Primary non-function occurs in 3 or more consecutive subjects at 2 or more participating clinical sites. Primary non-function (PNF) is defined by undetectable cpeptide levels (1-3 hours post-prandial) between 3-7 days post transplant;
- 3. There are 6 consecutive study subjects with a c-peptide less than 0.3 ng/mL (on random testing, at baseline and 1-3 hrs post MMTT) at 75 days post-transplant;
- 4. Any event(s) which in the opinion of the Medical Monitor or Protocol Chair indicates the need for DSMB review; or
- 5. The DSMB recommends termination of protocol enrollment and further transplants on a study-wide basis based on a review of the data and finding evidence that such action is necessary. Statistical guidelines for terminating the study based on monitoring guidelines are provided in section 10.

After the protocol is placed on hold, no additional transplants within the trial will be performed at any participating clinical site until the CIT Steering Committee and DSMB meet either in person or by conference call to review in depth the results and circumstances surrounding the islet functional failure or SAE to determine whether the trial enrollment of new subjects and conduct of additional transplants could be safely resumed.

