# 6.2.2 Site Suspension and Review

Study enrollment and initial islet transplants will be suspended (placed on hold) at a participating clinical site, pending expedited review of all pertinent data by the IRB, the NIAID, the NIDDK, and the NIDDK DSMB, if any one of the following occurs:

- 1. Any possibly study-related grade 5 AE; or
- 2. Two SAEs related to the islet transplant procedure (*e.g.* bleeding, thrombosis, gall bladder injury); or
- 3. Two consecutive primary non-functioning transplants defined by undetectable c-peptide levels (1-3 hours postprandial) between 3-7 days post transplant.

After any site is placed on hold, no additional transplants will be performed at that site until the CIT Steering Committee and DSMB meet either in person or by conference call to review in depth the results and circumstances surrounding the islet functional failure or SAE to determine whether the trial enrollment of new subjects and conduct of additional transplants could be safely resumed at that site, or whether there could be implications for the continuation of the entire proposed pilot protocol also at other affiliated sites testing the same protocol.

In all cases of PNF, subjects will be asked to temporarily continue immunosuppression to decrease the risk of sensitization that could increase the risk of poor outcome should future transplants occur. A tapering schedule will be applied until immunosuppressants are completely discontinued.

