#### 7.7 Visit Windows

The visit for determining the primary endpoint of insulin-independence will occur at  $75 \pm 5$  days following each islet transplant. All other visits are scheduled on a monthly basis from the last transplant (for the first 9 months; quarterly thereafter  $\pm$  14 d until 24 months, then biannually  $\pm$  30 d), and should occur within 7 days (plus or minus) of the calendar date for the transplant. For example, a subject receiving a transplant on the  $14^{th}$  of one month should have follow-up visits between the  $7^{th}$  and  $21^{th}$  of subsequent months. A second transplant resets this schedule, except for the retinal photography.

Study visits should take place within the time limits specified on the Schedule of Events (Appendix 1).

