# 10.2 Study Endpoint Assessment

# 10.2.1 Primary Endpoint

The primary objective of the analysis is to estimate the rate of insulin independence at 75 days after the first Islet Transplant among those in the study. The primary endpoint is insulin independence (yes/no) at day 75 after Islet Transplant as defined in section 3.1. The primary analysis will compute an exact binomial estimate and a 95% confidence interval for the true rate.

The primary endpoint should be available for all randomized subjects. An exception will be if a death occurs or if the subject withdraws consent to be followed, in these cases the endpoint will be classified as failure to achieve insulin independence. Should the endpoint not be evaluated for a particular individual for other reasons, a failure will be imputed unless an evaluation is done at a time longer than 75 days after transplant and before an additional islet transplant, in which case that later value will be imputed. All imputations will be reported with the primary analysis.

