#### REDUCED FOLLOW-UP SCHEDULE

Complete the following assessments at the intervals (+/-7 days) indicated below relative to the day the subject discontinued study treatment. Continue conducting these assessments at the defined intervals until the subject reaches one year post **last** transplant.

- Assess SAEs and hypoglycemic events: q1 month. If subject does not come to the study site for the visit, attempt to obtain information via a phone contact.
- Alloantibody (central lab): q 1 month for the first 3 months and q 3 months thereafter.

Complete the following assessments at 1 year (+/- 14 days) post **initial** transplant:

- Assess SAEs and hypoglycemic events
- Alloantibody (central lab)
- HbA1c (central lab)
- 90 minute c-peptide post MMTT (central lab)
- Serum creatinine (central lab)
- QOL questionnaire (via mail or in-person)

Complete the following assessments at 1 year (+/- 7 days) post **last** transplant:

- Assess SAEs and hypoglycemic events
- QOL questionnaire (via mail or in-person)

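### The reduced follow-up schedule in Appendix 2 has no Day 75 assessment, so a subject who fully stops study treatment before Day 75 can lose most Day 75 secondary efficacy data

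*Protocol*

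**What the plan says.** Section 5.7.2 keeps subjects who stop study treatment in the study "for the purpose of monitoring safety and efficacy parameters and will enter the reduced follow-up schedule outlined in Appendix 2", and it keeps their data in the intent-to-treat analysis. Section 4.3.1 says the same about purpose and analysis.

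Appendix 2 sets the timing: "All reduced follow-up assessments should be scheduled relative to the day on which the study treatment is discontinued". Until one year after the initial transplant it lists only SAEs, hypoglycemic events and alloantibody. HbA1c, a 90-minute C-peptide and serum creatinine appear once, at that one-year visit.

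Section 7.7 states: "The visit for determining the primary endpoint of insulin-independence will occur at" 75 ± 5 days after each transplant. Section 7.6 describes that visit: a week of capillary readings, HbA1c, fasting glucose and C-peptide, and 90-minute values after the test meal. Section 3.1.1 names one exception to Day 75 collection. When a third transplant follows the second by less than 75 days, "the 75 day endpoint data for the second transplant will not be collected". Stopped treatment is not named as an exception.

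On missing data, section 10.2.1 covers the primary endpoint: "a failure will be imputed unless an evaluation is done at a time longer than 75 days after transplant" and before another transplant. Section 10.2.2 rules out imputation for missing secondary endpoints and asks only that their frequency be reported.

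**The concern.** The protocol promises efficacy follow-up for subjects who stop treatment, then sends them to a schedule that collects no efficacy data at the trial's main time point. Some of the reasons for stopping are linked to outcome. Graft failure is a listed reason in section 5.7.2. After primary non-function, section 6.2.2 says: "A tapering schedule will be applied until immunosuppressants are completely discontinued".

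If such a subject is fully off treatment before Day 75 and Appendix 2 is followed, the Day 75 graft-function summaries are computed without a subject who has no graft function. These measures support the primary result, and the sample is 12, so even one such omission is visible. A later analysis plan cannot recover samples that were never drawn.

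**Working it through.** The plan gives no figure on this point. The only related number is the sample size of 12 in section 10.4. The table there concerns the primary endpoint, which is not affected; its entry for 6 of 12 (0.21 to 0.79) reproduces as 0.211 to 0.789.

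**Endpoints at risk (first transplant).** Section 3.1.1 lists 12 efficacy endpoints at Day 75: insulin independence, percent reduction in insulin, HbA1c, MAGE, LI, HYPO, MMTT glucose and C-peptide, beta-score, C-peptide ratio, the FSIGT measures, the CGMS measures and QOL. Insulin independence after the first transplant is the primary endpoint and is imputed under section 10.2.1. That leaves 12 − 1 = 11.

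**Can full discontinuation come before Day 75?** Primary non-function is defined at days 3 to 7 (section 6.2.2). The Day 75 window opens at day 70. A taper completed within 70 − 7 = 63 to 70 − 3 = 67 days of detection would end before the window opens. The length of the taper is not stated, so this is possible but not established.

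**Gap to the next metabolic value.** The shortest gap is (365 − 14) − (75 + 5) = 271 days. The longest is (365 + 14) − (75 − 5) = 309 days.

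**Size of the shift when the omitted subjects have no graft function.** Section 9.1.2.6 sets the beta-score at 0 without graft function. If k of 12 such subjects are left out, the sum of scores is unchanged and the divisor falls from 12 to 12 − k, so the mean is multiplied by 12/(12 − k). The value of k is an assumption, shown over a range:

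- k = 1: 12/11 = 1.091, or +9%
- k = 2: 12/10 = 1.200, or +20%
- k = 3: 12/9 = 1.333, or +33%

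The same factor holds approximately for C-peptide, which is near zero in these subjects, and for the ratio that has C-peptide as its numerator (section 9.1.2.7).

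**Endpoints recovered by keeping the visit.** The visit and its blood sugar record give percent insulin reduction, HbA1c, MAGE, MMTT values, beta-score, C-peptide ratio and QOL: 7 of 11. LI needs four or more readings a day over 4 weeks, and HYPO needs 4 weeks of recorded readings (sections 9.1.2.3 and 9.1.2.4). With that record the count is 9 of 11. FSIGT and CGMS stay missing.

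**The case against.** The strongest reply is that the Day 75 visit may still take place. Sections 7.6 and 7.7 schedule it after each transplant, section 10.2.1 expects the primary endpoint for all randomized subjects, and section 3.1.1 makes only one exception. This stands as evidence of conflicting instructions. It does not settle the matter, because section 5.7.2 and Appendix 2 explicitly move these subjects to another schedule and give no rule of precedence.

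The second reply concerns frequency, and it stands. After primary non-function, immunosuppression continues temporarily (section 6.2.2). Section 7.5.1 considers a second transplant only after the Day 75 metabolic assessment, and it withdraws immunosuppression for absent function only after a second transplant has failed. Full discontinuation before Day 75 is therefore not the usual first-transplant course.

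Third, three of the four reasons for stopping in section 5.7.2 do not require graft loss. A reader might infer that every early stopper inflates the Day 75 results. The documents do not support that, because subjects who stop for non-compliance, investigator judgment or a related SAE may have a functioning graft.

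A reader might also infer that the third suspension rule in section 6.2.1 fails: "There are 6 consecutive study subjects with a c-peptide less than 0.3 ng/mL" at 75 days. A missing value is possible there, and the rule does not say how to count it. But two consecutive primary non-functions already suspend the site under section 6.2.2. Graft failure is itself diagnosed by a core-laboratory meal test (section 5.7.2), and the Medical Monitor or Protocol Chair can call for DSMB review of any event. Failure of the rule is not shown.

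Finally, the frequency of missing data will be reported, and section 10.2.2 advises extreme caution with nominally significant secondary results. Reporting shows the gap but does not fill it, and the caution concerns Type I error.

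**Conclusion.** The point holds as a conditional gap in the secondary data. Followed as written, Appendix 2 leaves a subject who has fully stopped before Day 75 without up to 11 of the 12 Day 75 secondary efficacy endpoints and with no metabolic value for another 271 to 309 days. The protocol does not say whether Appendix 2 or sections 7.6 and 7.7 govern.

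Where the reason is graft failure or primary non-function, the Day 75 beta-score, C-peptide and C-peptide ratio are biased upward, by about 9% in mean beta-score for one such subject of 12. This assumes that all 12 are transplanted, that the omitted score is 0 and that Appendix 2 is applied. The number of such subjects cannot be derived from the documents.

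Three wider conclusions might be inferred but are not supported:

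- The primary result is not affected, because a failure is imputed.
- The direction for HbA1c is not fixed.
- The effect on the comparison with CIT-07 depends on that study's follow-up rules, which are not shown.

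**What to change.** Add to Appendix 2: if study treatment stops before Day 75 after a transplant, the following are still collected at Day 75 ± 5: HbA1c, fasting and 90-minute MMTT glucose and C-peptide, serum creatinine, the insulin and blood sugar record (with the preceding 4 weeks of readings where LI and HYPO are to be computed), and QOL. This also settles which schedule governs. The timing of any taper stays with the site.

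The cost is one extra visit per affected subject, using tests already scheduled at Day 75 in Appendix 1, plus continued glucose logging for 4 weeks if LI and HYPO are wanted. It needs no extra subjects and no added immunosuppression.
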